**Table 11-1 Acceptable PK Sampling Windows**

Sampling Time	Time From Sampling Schedule Allowed
Pre-dose	Within 60 minutes before study drug dose on PK sampling days
2, 3, 6, and 8 hours after study drug dosing	± 30 minutes

PK: pharmacokinetic.

### **11.4.2 Processing and Handling of Pharmacokinetic Samples**

Detailed procedures for the collection of blood samples, and further procedures for processing and handling of samples for PK analysis, will be provided in the Laboratory Manual. The shipment address and assay laboratory contact information will be provided to the investigational site before initiation of the study.

### **11.4.3 Bioanalysis**

Samples will be analyzed using a validated analytical method in compliance with Vertex or designee standard operating procedures. A description of the assay methods and validation data will be provided in separate reports.

If appropriate, these samples may also be used for evaluations of metabolites of VX-661 and ivacaftor during treatment. These samples may also be used for further evaluation of the bioanalytical method and for analyses that provide information on the metabolic pathways used or impacted by VX-661 and ivacaftor. These data will be used for exploratory purposes and may not be included in the clinical study report.

## 11.6 Efficacy

### 11.6.1 Spirometry

Spirometry will be performed according to the ATS/ERS guidelines at the time points noted in [Table 3-1](#) and [Table 3-2](#) according to the additional guidelines that follow.

Prebronchodilator spirometry is defined as spirometry testing performed for subjects who have

- withheld their short-acting bronchodilators (e.g., albuterol) or anticholinergic (e.g., ipratropium bromide [Atrovent®]) for more than 4 hours before the spirometry assessment;
- withheld their long-acting bronchodilator (e.g., salmeterol) for more than 12 hours before the spirometry assessment; and
- withheld their once-daily, long-acting bronchodilator (e.g., tiotropium bromide [Spiriva®]) for more than 24 hours before the spirometry assessment.

During the treatment periods (both Ivacaftor Run-in Period and the Active Comparator Treatment Period), spirometry assessments must be performed before dosing. In adolescent subjects (<18 years of age at the Screening Visit) additional postdose spirometry assessments on Day 1 and Day 15 will be performed at 2 and 4 hours after the morning dose as a safety assessment. A window for  $\pm 15$  minutes will be allowed around the nominal times for all postdose spirometry assessments.

During the Screening Period, spirometry assessments may be performed pre- or postbronchodilators. At all other visits, all spirometry assessments should be performed “prebronchodilator.”

In the event that a subject does not withhold his/her bronchodilator(s), spirometry should be performed according to the following:

#### During the Ivacaftor Run-in Period

- If a subject's Week -4 spirometry is prebronchodilator, but, on a subsequent visit during the Ivacaftor Run-in Period, the subject does not withhold bronchodilator use, a postbronchodilator spirometry will be obtained for that visit only, and the visit will not be rescheduled.
- If, on Week -4, the subject does not withhold his/her dose of bronchodilator, spirometry should be performed postbronchodilator, and subsequent spirometric measurements during the Ivacaftor Run-in Period (according to the schedule of assessments detailed in [Table 3-2](#)) should be performed postbronchodilator.

#### During the Active Comparator Treatment Period

- If a subject's Day 1 spirometry is prebronchodilator, but, on a subsequent visit during the Active Comparator Treatment Period, the subject does not withhold bronchodilator use, a postbronchodilator spirometry will be obtained for that visit only, and the visit will not be rescheduled.

- If, on Day 1, the subject does not withhold his/her dose of bronchodilator, spirometry should be performed postbronchodilator, and all subsequent spirometric measurements during the Active Comparator Treatment Period (according to the schedule of assessments detailed in [Table 3-2](#)) should be performed postbronchodilator.
- Spirometry assessments that occur after dosing (postdose) on Day 1 and Day 15 (for subjects <18 years of age at the Screening Visit) should be performed prebronchodilator. If Day 1 and/or Day 15 predose spirometry is performed postbronchodilator, the subject should withhold any further bronchodilator use until after completion of the 4-hour postdose spirometry assessment on that day.
- For both Ivacaftor Run-in Period and the Active Comparator Treatment Period, each spirometry assessment will be recorded in the source documents as pre- or postbronchodilator.

All sites will be provided with spirometers to be used for all study assessment. Spirometry data will be transmitted to a centralized spirometry service for quality review.

Subjects and their parent/caregiver should not be informed of their study-related spirometry results during the Active Comparator Treatment Period (Day 1 through Week 8), regardless of whether the subject prematurely discontinues treatment.

The parameters listed below will be normalized using the standards of Wang et al (for female subjects aged 12 to 15 years [inclusive] and male subjects aged 12 to 17 years [inclusive]) or Hankinson et al (for female subjects aged 16 years and older and male subjects aged 18 years and older).

- FEV1 (L)
- Forced vital capacity (FVC) (L)
- FEV1/FVC (ratio)
- Forced expiratory flow (L/s)

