9 STATISTICAL ANALYSIS

9.1 General Considerations

The Schedule of Assessments is provided in [Appendix C](#). The precision standards for reporting safety and efficacy variables are provided in an internal Biometrics document that specifies the programming rules including the precision for derived variables.

All individual subject data for subjects who were randomized or received at least 1 dose of study drug, i.e., All Subjects Set, will be presented in data listings, with indicator of dosing period, i.e., Ivacaftor Run-in Period vs. Active Comparator Treatment Period, as applicable. Listings related to Active Comparator Treatment Period only will be based on the Active Comparator Subjects Set.

Continuous variables will be summarized using the following descriptive summary statistics: the number of subjects (n), mean, standard deviation (SD), standard error (SE), median, minimum value (min), and maximum value (max).

Categorical variables will be summarized using counts and percentages.

Baseline value, Absolute change from baseline and Relative change from baseline will be defined separately for the Ivacaftor Run-in Period and the Active Comparator Treatment Period:

Baseline value:

- Unless specified otherwise, baseline for the Ivacaftor Run-in Period will be defined as the most recent non-missing measurement (scheduled or unscheduled) collected prior to initial administration of Ivacaftor monotherapy.
- Unless specified otherwise, the baseline for the Active Comparator Treatment Period will be defined as the most recent non-missing measurement (scheduled or unscheduled) collected prior to initial administration of the VX-661/ivacaftor combination therapy or ivacaftor monotherapy (placebo/ivacaftor) during the Active Comparator Treatment Period, but no earlier than the measurement at Week -2.
- For spirometry, the baseline value used for the Active Comparator Treatment Period will be the average of the measurement at Week -2 and the measurement on Day 1 predose. If a subject has an AE leading to an approved extension of the Ivacaftor Run-in Period, and the Week -2 spirometry assessment is between the start and end date (inclusive) of the AE, then the measurement on Day 1 predose will serve as baseline for the Active Comparator Treatment Period.
- For ECG, the baseline will be defined as the average of the non-missing pretreatment measurements (triplicate) on Day 1 (the first day) of the corresponding treatment period.

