9.4.6 Postdose Spirometry

For the 2-hour and 4-hour postdose spirometry measurements on Day 1 and Day 15, a summary of raw values for percent predicted FEV1 will be provided by treatment group at each time point. The absolute change from the predose value of percent predicted FEV1 on the same day will be provided by treatment group at each time point. In addition, a boxplot by time point will be provided. Within each treatment group, Day 1 and Day 15 values will be presented on the same plot.

The above analyses will be repeated for FEV1.

In addition, the number and percentage of subjects with percent predicted FEV1 decline ≥ 10 , ≥ 15 , and ≥ 20 percentage points in the absolute change from the predose value will be summarized by treatment group and by assessment day and time.

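### Bronchodilator status is not used in SAP 9.4.6 or 9.1, so bronchodilator wear-off can count as postdose FEV1 decline in some adolescents and a few baselines can average unlike tests

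*Protocol*

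**What the plan says.** **Default and departures.** Protocol 11.6.1 makes prebronchodilator spirometry the rule after screening. For a short-acting agent this means withholding it "for more than 4 hours before the spirometry assessment"; for long-acting and once-daily agents the limits are 12 and 24 hours. The section also says what to do when a subject has not withheld. In the run-in, a single visit may be postbronchodilator, or a postbronchodilator Week -4 test sets the status for the rest of the run-in. Day 1 then sets status afresh: "If, on Day 1, the subject does not withhold his/her dose of bronchodilator, spirometry should be performed postbronchodilator", and later tests in the period follow it. Finally, "each spirometry assessment will be recorded in the source documents as pre- or postbronchodilator".

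**Postdose tests.** In subjects under 18, extra tests on Day 1 and Day 15 "will be performed at 2 and 4 hours after the morning dose as a safety assessment". Protocol 11.6.1 says these "should be performed prebronchodilator". For a subject whose predose test was not, it adds: "If Day 1 and/or Day 15 predose spirometry is performed postbronchodilator, the subject should withhold any further bronchodilator use" until the 4-hour test is complete.

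**Analysis.** SAP 9.4.6 states: "The absolute change from the predose value of percent predicted FEV1 on the same day will be provided by treatment group". It also counts subjects with declines of at least 10, 15 and 20 percentage points from predose. Protocol 12.3.4.6.2 matches. Neither sets a condition on bronchodilator status.

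**Baseline.** SAP 9.1 defines the spirometry baseline as "the average of the measurement at Week -2 and the measurement on Day 1 predose". The only exception is a Week -2 test taken during an AE that led to an approved run-in extension; Day 1 predose is then used alone.

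**The concern.** A predose test done under bronchodilator is raised by the bronchodilator response. With further use withheld, that response can wane at 2 and 4 hours. The subject's measured change is then any drug effect, plus measurement noise, minus the response lost. SAP 9.4.6 reads the whole of it as postdose change. The reverse mix should not arise, because the schedule withholds bronchodilators until the last scheduled test of the visit. The error therefore has one direction, toward apparent decline. Protocol 8.2.4 says these tests meet a regulator's request, so the absolute decline counts are likely to be read as well as the difference between arms.

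The baseline issue has the same root. The run-in status rules do not bind Day 1, so Week -2 and Day 1 can differ in status and are still averaged. The resulting baseline matches neither a prebronchodilator nor a postbronchodilator series of later tests.

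**Working it through.** **1. The plan's own power figure.** Inputs from SAP 7.2: 160 subjects, 10% dropout (160 × 0.9 / 2 = 72 per arm), difference 3.4, SD 7, two-sided 0.05. Power ≈ Φ(3.4 / (7 × √(2/72)) − 1.96) = 83.0%, which agrees with the stated minimum of 80%. This is the reference for step 4.

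**2. Can the postdose mismatch occur?** Yes. Protocol 11.6.1 names the case (predose postbronchodilator on Day 1 or Day 15) and gives an instruction for it. SAP 9.4.6 has no rule for it.

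**3. Size for one affected adolescent.** The documents give neither the within-day SD (s) nor the bronchodilator response, so both are assumed. Let w be the points of response lost by the time of the test. With no true drug effect, P(fall ≥ T) = Φ((w − T) / s).

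| w (points lost) | s | T = 10 | T = 15 | T = 20 |
|---|---|---|---|---|
| 0 | 4 | 0.6% | <0.1% | <0.1% |
| 0 | 5 | 2.3% | 0.1% | <0.1% |
| 3 | 4 | 4.0% | 0.1% | <0.1% |
| 3 | 5 | 8.1% | 0.8% | <0.1% |
| 5 | 4 | 10.6% | 0.6% | <0.1% |
| 5 | 5 | 15.9% | 2.3% | 0.1% |
| 8 | 4 | 30.9% | 4.0% | 0.1% |
| 8 | 5 | 34.5% | 8.1% | 0.8% |

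A response of 3 to 8 points that is lost in full gives 4–34% at the 10-point threshold. For scale, with w = 5 and s = 4, ten affected subjects would yield 10 × (0.1056 − 0.0062) ≈ 1 extra fall of at least 10 points at a given test time.

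These are upper bounds. By the protocol's own windows, a short-acting agent taken shortly before the predose test still counts as active at 2 hours, and the 12- and 24-hour agents still count at 4 hours. Full loss fits best for a short-acting agent at the 4-hour test; elsewhere w is less than the full response.

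**4. Baseline mixing.** Let b be the bronchodilator response.
- Week -2 pre, Day 1 and later tests post: baseline is too low by b/2, so change is too high by b/2.
- Week -2 post for that visit only, Day 1 and later tests pre: baseline is too high by b/2, so change is too low by b/2.

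For b = 3, 5 or 10 the shift is 1.5, 2.5 or 5 points. If a share p of subjects is shifted in one direction, the added variance is p(1 − p)(b/2)². With p = 5–20% and b = 3–10 (both assumed), it is 0.05 × 0.95 × 1.5² = 0.11 to 0.20 × 0.80 × 5² = 4.0. The SD rises from 7.00 to √49.11 = 7.01 at the least and √53 = 7.28 at the most. Power goes from 83.0% to between 82.9% and 80.0%.

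If the two directions are equally common, the added variance is p(b/2)². The extreme corner is then 0.20 × 25 = 5, giving SD √54 = 7.35 and power 79.3%.

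**5. An inconsistency in Protocol 11.6.1.** One bullet makes all measurements in the period after a postbronchodilator Day 1 test postbronchodilator. The next calls for prebronchodilator postdose tests on Day 1 and Day 15. For a subject who did not withhold on Day 1, both cannot be followed as written. The 4-hour definition sharpens this: a 2-hour test after recent short-acting use is still postbronchodilator.

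**The case against.** The strongest reply is that this concerns departures only. Prebronchodilator testing is required at every visit after screening. The postdose issue reaches only subjects under 18 who failed to withhold on Day 1 or Day 15, and no document says how many that will be. The table is descriptive, SAP 9.4 rules out safety testing, and the ivacaftor arm carries the same artefact, so the comparison between arms is largely protected. All of this stands and limits the point to a minor improvement. It does not make the absolute counts interpretable for affected subjects.

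A reader might infer that wear-off would be reported as a drug-related decline. The documents do not support that: SAP 9.4.6 summarises by arm and attributes nothing to drug. A reader might also take 34% as a typical rate, but it rests on an assumed response and on full wear-off.

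On baseline, a reader might infer a systematic artificial gain, or a threat to the primary result. Neither follows. The error can go either way, both tests precede randomized dosing so it is unrelated to arm in expectation, and the SAP 9.3.1.3 model adjusts for baseline percent predicted FEV1.

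Finally, SAP text between 9.3.1.3 and 9.3.2 is removed from the public version. A sensitivity analysis of the primary endpoint by bronchodilator status may sit there, so it cannot be said that the whole SAP disregards status. Sections 9.1 and 9.4.6 are visible and contain no such rule.

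**Conclusion.** The point holds as a minor one. For adolescents whose Day 1 or Day 15 predose test was postbronchodilator, SAP 9.4.6 measures change and decline from a raised value, and the error is toward apparent decline. At most, and under assumed inputs, the chance of a fall of at least 10 points rises from 0.6–2.3% to 4–34% per affected subject. The effect at 15 and 20 points is much smaller. The number affected is unknown and probably small, and both arms are exposed.

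The SAP 9.1 baseline rule shifts a discordant subject's change by half the bronchodilator response, in either direction. It adds a little noise and no expected bias to the treatment contrast. Even with 20% of subjects discordant and a 10-point response, power stays at about 80% against 83.0%.

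**What to change.** 1. **SAP 9.4.6:** base the main postdose change and decline counts on subjects whose same-day predose test was prebronchodilator. Show the remaining subjects in a separate row or listing, so that no safety data are lost. Requiring only that predose and postdose status match would not work: a 2-hour test soon after a short-acting dose is still postbronchodilator, would match, and would keep the partial wear-off.
2. **SAP 9.1:** when Week -2 and Day 1 status differ, use the Day 1 predose value alone. The SAP already does this for some AE-related run-in extensions, and Day 1 status is the one that later tests are meant to follow.
3. **Data:** carry the pre/post status of each test into the analysis data. The protocol promises it only in source documents.
4. **Protocol 11.6.1:** reconcile the two statements on the status of tests that follow a postbronchodilator Day 1 test.

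Cost: SAP wording settled before database lock, a small data-transfer task, a slightly smaller main postdose table, and loss of baseline averaging for a few subjects. Protocol 12.3.1 and 12.3.4.6.2 carry the same rules, so the SAP should record the changes as departures from them.

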### **11.6.2 Sweat Chloride Testing**

The sweat chloride test is a standard diagnostic tool for CF, serving as a biomarker of CFTR activity. Collection of sweat samples will be performed at visits specified in [Table 3-1](#) and [Table 3-2](#), using an approved collection device. Sweat samples will be sent to a central laboratory for testing and interpretation of results. Individual sweat chloride test results will not be disclosed to the study sites. Specific instructions for collection, handling, processing, and shipping of sweat chloride samples to the central laboratory will be provided separately.

The sweat chloride collection on dosing days should occur before the morning dose of the study drugs. At each time point, 2 samples will be collected, 1 from each arm (left and right). Additionally, sweat chloride collection will be performed at the Screening Visit and the ETT Visit. For subjects using sweat chloride values documented in their medical records to establish eligibility, the sweat chloride test at the Screening Visit is optional. Collection of sweat chloride will not overlap with any other study assessments.

### 11.6.3 Cystic Fibrosis Questionnaire-Revised

Subjects will be asked to complete the CFQ-R in their native language. The CFQ-R will be completed before the start of any other assessments, as noted in [Table 3-1](#) and [Table 3-2](#). At all visits, subjects who are 12 and 13 years of age at Week -4 will complete the CFQ-R Child version themselves, and their parents/caregivers will complete the CFQ-R Parent version, regardless of whether the subject subsequently turns 14 years of age during the study. Subjects 14 years of age and older at Week -4 will complete the Adolescent/Adult version of the questionnaire themselves at all visits. The questionnaires provide information about demographics; general quality of life, school, work, or daily activities; and symptom difficulties (pertaining to CF). Copies of the CFQ-R used in this study will be provided in the Study Reference Manual. Validated translations of the CFQ-R will be provided for participating centers in non-English-speaking countries.

## **11.7 Safety**

Safety evaluations will include AEs, clinical laboratory assessments, clinical evaluation of vital signs, ECGs, pulse oximetry, spirometry, PEs, and ophthalmologic exams.

### **11.7.1 Adverse Events**

All AEs will be assessed, documented, and reported in accordance with ICH GCP guidelines. [Section 13.1](#) outlines the definitions, collection periods, criteria, and procedures for documenting, grading, and reporting AEs. A separate document that details AE electronic case report form completion guidelines for investigators as well as training will be provided.

### **11.7.2 Clinical Laboratory Assessments**

Blood and urine samples will be analyzed at a central laboratory, with the exception of urine pregnancy tests, which are performed and analyzed at the site. Blood samples requiring a 4-hour fast will be collected on Day 1, Week 8, the ETT, and the Safety Follow-up Visit. Fasting is not required at other time points unless specified in the assessment table. At the Week -4 and Day 1 Visits, blood samples will be collected before the first dose of the study

drug. At all other scheduled visits, these samples will be collected at any time during the visit, relative to the order of assessments indicated in [Section 11.1](#) and according to the schedule of assessments in [Table 3-1](#) and [Table 3-2](#).

Blood and urine samples for clinical laboratory assessments will be collected as shown in [Table 3-1](#) and [Table 3-2](#). Laboratory test results that are abnormal and considered clinically significant will be reported as AEs ([Section 13.1.1](#)).

The safety laboratory test panels are shown in [Table 11-2](#).

**Table 11-2 Safety Laboratory Test Panels**

Serum Chemistry	Hematology	Urinalysis a
Glucose	Hemoglobin	Leukocyte esterase
Blood urea nitrogen	Erythrocytes	Nitrite
Creatinine	Mean corpuscular hemoglobin	Urobilinogen
Sodium	Mean corpuscular hemoglobin concentration	Urine protein
Potassium	Mean corpuscular volume	pH
Calcium	Reticulocytes	Urine blood
Chloride	Platelets	Specific gravity
Magnesium	Leukocytes	Urine ketones
Bicarbonate	Differential (absolute and percent):	Urine bilirubin
Inorganic phosphate	Eosinophils	Urine glucose
Total bilirubin, direct bilirubin	Basophils	
Alkaline phosphatase	Neutrophils	
Aspartate aminotransferase	Lymphocytes	
Alanine aminotransferase	Monocytes	
Lactate dehydrogenase	Coagulation Studies	
Gamma-glutamyl transpeptidase	Activated partial thromboplastin time	
Total protein	Prothrombin time	
Albumin	Prothrombin time International Normalized Ratio	
Creatine kinase		
Amylase		
Lipase		
Vitamin Levels		
Vitamin levels A, D, E, K, B12		
Lipid Panel		
Total cholesterol, triglycerides		
Low-density lipoprotein		
High-density lipoprotein		

a If urine is positive for leukocyte esterase, nitrite, protein, or blood, microscopic examination of urine will be performed for leukocytes, erythrocytes, crystals, bacteria, and casts.

Pregnancy (β-human chorionic gonadotropin) Tests for Females of Childbearing Potential: Serum samples will be obtained as specified in [Table 3-1](#) and [Table 3-2](#) and analyzed at the central laboratory. Urine pregnancy tests will be performed at the site as specified in [Table 3-2](#). The urine pregnancy test at the Week -4 Visit must be negative before the first dose of study drug.

Follicle-stimulating Hormone (Screening Period only): Blood sample for FSH will be measured for any potentially postmenopausal female with at least 12 months of continuous spontaneous amenorrhea. Serum FSH levels must be  $\geq 40$  mIU/mL to be considered postmenopausal.

CFTR Genotype (Screening Period only): CF genotyping will be performed on all subjects to confirm the genotype documented in the subject's medical record. The results of the confirmatory genotype sample obtained at the Screening Visit must be reviewed before enrollment. In patients with confirmed *R117H* mutation, linkage to poly-T track polymorphisms will also be determined. Specific instructions will be provided in the Laboratory Manual.

Additional Evaluations: Additional clinical laboratory evaluations will be performed at other times if judged to be clinically appropriate.

For purposes of study conduct, only laboratory tests done in the central laboratory may be used. At the discretion of the local investigator, local laboratories may be used for management of urgent medical issues. If a local laboratory test value is found to be abnormal and clinically significant, it should be verified by the central laboratory as soon as possible after the investigator becomes aware of the abnormal result. If it is not possible to send a timely specimen to the central laboratory (e.g., the subject was hospitalized elsewhere), the investigator may base the assessment of an AE on the local laboratory value.

